Results from a Phase 3, multicenter, randomized, crossover study in subjects with MDS/CMML or acute myeloid leukemia (AML) (ASTX727-02) established AUC equivalence of the FDC tablet (35 mg decitabine and 100 mg cedazuridine) with IV administered decitabine (20 mg/m^2). Assessment of efficacy indicated that the best response of CR was observed in 21.8% of all treated subjects and in 24.8% of subjects evaluable for response. Marrow CR was achieved in 32.3% of all treated subjects and in 36.8% of subjects evaluable for response. The overall response rate

(ORR; complete response [CR] + partial response [PR] + marrow CR [mCR] + HI) was 61.7% in all treated subjects and 70.1% in subjects evaluable for response. In addition, mCR with HI was reported in 16.5% of all treated subjects and in 18.8% of subjects evaluable for response. Sixteen subjects (12%) were not evaluable for response. With respect to the rate of subjects who were transfusion independent for  $\geq 56$ ,  $\geq 84$ , and  $\geq 112$  consecutive days at any time post-baseline for subjects who were transfusion dependent at baseline, more than half (51.9%) of the 54 subjects who were RBC transfusion dependent at baseline were RBC transfusion independent for any consecutive  $\geq 56$ -day period post-baseline. A similar overall rate of platelet TI (50%) for any consecutive  $\geq 56$ -day period post-baseline was observed for subjects with platelet transfusion dependence at baseline. Rates of RBC and platelet TI were 40.7% and 33.3%, respectively, for  $\geq 84$  consecutive days and leveled at 33.3% for  $\geq 112$  consecutive days. The overall incidence of common adverse events (AEs) of thrombocytopenia, neutropenia, anemia, and febrile neutropenia observed in Phase 2 and Phase 3 was generally similar between oral decitabine/cedazuridine and IV decitabine.

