Results from a Phase 3, multicenter, randomized, crossover study in subjects with MDS/CMML or AML (ASTX727-02) established AUC equivalence of the FDC tablet (35 mg decitabine and 100 mg cedazuridine) with IV administered decitabine ( $20 \text{ mg/m}^2$ ). Assessment of efficacy indicated that the best response of CR was observed in 21.8% of all treated subjects and in 24.8% of subjects evaluable for response. Marrow CR was achieved in 32.3% of all treated subjects and in 36.8% of subjects evaluable for response. The ORR (CR + PR + mCR + HI) was 61.7% in all treated subjects and 70.1% in subjects evaluable for response. In addition, mCR with HI was reported in 16.5% of all treated subjects and in 18.8% of subjects evaluable for response. Sixteen subjects (12%) were not evaluable for response. With respect to the rate of subjects who were transfusion independent for  $\geq 56$ ,  $\geq 84$ , and  $\geq 112$  consecutive days at any time post-baseline for subjects who were transfusion dependent at baseline, more than half (51.9%) of the 54 subjects who were RBC transfusion dependent at baseline were RBC transfusion independent for any consecutive  $\geq 56$ -day period post-baseline. A similar overall rate of platelet TI (50%) for any consecutive  $\geq 56$ -day period post-baseline was observed for subjects with platelet transfusion dependence at baseline. Rates of RBC and platelet TI were 40.7% and 33.3%, respectively, for  $\geq 84$  consecutive days and leveled at 33.3% for  $\geq 112$  consecutive days. The overall incidence of common adverse events (AEs) of thrombocytopenia, neutropenia, anemia, and febrile neutropenia observed in Phase 2 and Phase 3 was generally similar between oral decitabine/cedazuridine and IV decitabine. Further details can be found in the oral decitabine/cedazuridine IB.

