#### **8.3.1 Disease Response Assessment**

Disease assessment will follow IWG 2006 criteria ([Section 10.6](#)) and will include CR, HI, and ORR (including CR, mCR, or any HI). Other assessments will include duration of PFS, LFS, undetectable disease assessed by MRD, DOR, and OS. Disease response assessment will be determined based on BM evaluations and a corresponding PB sample along with transfusion requirements. Bone marrow evaluations must include aspirate (when feasible), biopsy, and cytogenetics. If hematologic recovery is in progress, a repeat CBC may be done no more than 7 days after the BM evaluation for response assessment. The BM biopsy and aspirate procedure will be conducted according to local standard practice at time points shown in the SoA ([Table 1](#)).

BM and PB samples adequate for analysis must be obtained in order to confirm response. BM biopsy and aspirate and a CBC must be repeated if the BM and/or PB sample are not interpretable by the investigator. A local laboratory will be used to assess BM and PB samples. BM samples should be Wright Giemsa or May Grunwald Giemsa stained. Detailed instructions for processing BM samples will be provided in the Laboratory Manual.

BM evaluations should be performed at screening and on Day 1 of every cycle (or within a 3-day window prior to Day 1) until an mCR is achieved (BM myeloblasts  $\leq 5\%$  and decrease by  $\geq 50\%$  over pretreatment). If an mCR is achieved, without meeting CR criteria, a follow-up BM evaluation should occur on Day 1 of the next cycle (or within a 3-day window prior to Day 1) to assess or confirm the possibility of CR. Thereafter, BM evaluation may occur as clinically indicated to monitor DOR as appropriately guided by PB counts after achieving a confirmed CR

but should occur at least every 3 cycles for the first year, then as clinically indicated. Results do not have to be fully available to start study treatment for that cycle.

Response will be assessed by the investigator and derived programmatically based on the 2006 IWG criteria ([Cheson et al 2006](#)). Further details of the IWG criteria can be found in Section [10.6](#).

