### 9.3.2 Primary Endpoint(s)

The primary efficacy endpoint for this study is the proportion of subjects who achieve CR. Response rate will be based on the investigator assessment for all treated subjects. Exact Clopper-Pearson 95% CI will be presented.

The analysis of duration of CR, ORR, OS, and PFS will be conducted using the Kaplan-Meier method based on subjects who achieved CR. Median duration of CR will be estimated with its 95% CI for each treatment arm based on the Kaplan-Meier method. For the time-to-event

endpoints of the duration of CR and DOR will be based on subjects who achieved ORR. The median duration will be estimated with its 95% CI for each treatment arm.

Analysis for all secondary efficacy endpoints will also be performed by pre-specified subgroups. Details of this analysis will be presented in the SAP.

No formal hypothesis testing will be conducted for any key secondary endpoint.

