**Table 21: Response Criteria in Myelodysplastic Syndromes (IWG 2006 Criteria)**

Category	Response Criteria (responses must last $\geq 4$ weeks)
CR	
 
• BM <math>\leq 5\%</math> myeloblasts with normal maturation of all cell linesa
 
• Persistent dysplasia will be noteda,b
 
• Peripheral bloodc
 
• Hgb <math>\geq 11</math> g/dL
 
• Platelets <math>\geq 100 \times 10^9/L</math>
 
• Neutrophils <math>\geq 1.0 \times 10^9/L^b</math>
 
• Blasts 0%
 

PR	All CR criteria if abnormal before treatment except: 
 
• BM blasts decreased by <math>\geq 50\%</math> over pretreatment but still <math>>5\%</math>
 
• Cellularity and morphology not relevant
 

Marrow CR	BM $\leq 5\%$ myeloblasts and decrease by $\geq 50\%$ over pretreatment b Peripheral blood: if HI responses, they will be noted in addition to marrow CR b
Stable Disease	Failure to achieve at least PR, but no evidence of progression for $>8$ weeks
Failure	Death during treatment or disease progression characterized by worsening cytopenias, increase in percentage of BM blasts, or progression to a more advanced MDS FAB subtype than pretreatment
Relapse after CR or PR	At least 1 of the following: 
 
• Return to pretreatment BM blast percentage
 
• Decrement of <math>\geq 50\%</math> from maximum remission/response levels in granulocytes or platelets
 
• Reduction in Hgb concentration by <math>\geq 1.5</math> g/dL or transfusion dependenced
 

Cytogenetic Response	Complete: Disappearance of chromosomal abnormality without appearance of new ones Partial: At least 50% reduction of the chromosomal abnormality

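### Duration of CR is given two incompatible analysis sets, and DOR covers all ORR responders although Table 21 defines relapse only after CR or PR, so DOR can be overstated on one reading of progression

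*Combined protocol and SAP*

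**What the plan says.** Section 9.3.2 states: "The analysis of duration of CR, ORR, OS, and PFS will be conducted using the Kaplan-Meier method based on subjects who achieved CR". Two sentences later it says that the time-to-event "endpoints of the duration of CR and DOR will be based on subjects who achieved ORR". Duration of CR thus appears with both sets.

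Section 8.3.1 describes the response rate as "ORR (including CR, mCR, or any HI"; Section 4.2 gives the same components. A subject with marrow CR or HI alone is therefore in the DOR set.

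In Table 21 (Section 10.6), a return of marrow blasts to the pretreatment level ends a response only in the row "Relapse after CR or PR". Two other rows apply to any subject:

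- Failure: death on treatment, or progression shown by worsening cytopenias, rising marrow blasts or a more advanced subtype. No size of rise is given.
- Disease Progression: a rise of at least 50% past a limit set by blast stratum, a fall of at least half from best response in granulocytes or platelets, an Hgb fall of at least 2 g/dL, or transfusion dependence.

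No section gives a start, event or censoring rule for DOR. Section 9.3 leaves technical detail to a later SAP.

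**The concern.** There are two separate problems. First, a duration-of-CR curve drawn on ORR subjects would include people who never had a CR, so it would not describe CR.

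Second, the DOR set is wider than the only relapse rule. Table 21 names its reference value elsewhere: pretreatment for the blast fall that defines marrow CR, and best response for the count criterion. It names none for the blast strata. Sections 6.3 and 8.3.1 say response is derived by program, and a program has to use one reference. If it uses pretreatment blasts, a subject whose marrow response is wholly lost can still be counted as responding.

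DOR is a named secondary endpoint, and Section 4.1 says study length may be adjusted on it.

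**Working it through.** The plan states no DOR median or event count, so there is no figure of its own to reproduce. The checks are on the rule, the share of responders it touches, and the possible size of the effect.

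**1. The blast rule applied to example courses.** Strata and limits are from Table 21. Blast progression requires later blasts of at least 1.5 × the reference and above the stratum's limit.

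| Pretreatment → lowest → later | Reference = pretreatment | Reference = lowest on-study |
|---|---|---|
| 12% → 3% → 12% | needs ≥18% and >20%: no | needs ≥4.5% and >5%: yes |
| 8% → 3% → 8% | needs ≥12% and >10%: no | needs ≥4.5% and >5%: yes |
| 12% → 4% → 6% | no | needs ≥6% and >5%: yes |
| 12% → 4% → 5.5% | no | 5.5/4 = 1.375, a 38% rise: no |
| 12% → 5% → 8% | no | 5%-10% stratum, needs ≥7.5% and >10%: no |

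Read from pretreatment, a return to the starting level is a 0% rise and never counts. Read from the lowest value, most losses of marrow CR count, with small gaps such as the last two rows. Section 8.3.2 adds a further description of progression for telephone contacts (marrow blasts of 5% or more and conversion to AML), which does not settle the reference either.

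**2. Share of responders affected, ASTX727-02 mix (Section 2.2).** Inputs: "The ORR (CR + PR + mCR + HI) was 61.7% in all treated subjects" (70.1% of evaluable); "Marrow CR was achieved in 32.3% of all treated subjects and in 36.8% of subjects evaluable for response"; "mCR with HI was reported in 16.5% of all treated subjects and in 18.8% of subjects evaluable for response"; CR 21.8% and 24.8%; 16 subjects not evaluable. Of all treated totals from 120 to 145, only 133 (117 evaluable) reproduces all eight percentages:

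- CR: 29/133 = 21.8%, 29/117 = 24.8%
- mCR: 43/133 = 32.3%, 43/117 = 36.8%
- mCR with HI: 22/133 = 16.5%, 22/117 = 18.8%
- ORR: 82/133 = 61.7%, 82/117 = 70.1%

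Taking the categories as exclusive best responses:

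- mCR share of responders: 43/82 = 52%.
- mCR without HI: (43 − 22)/82 = 26%.
- Responders without a CR: (82 − 29)/82 = 65%. The remaining 82 − 29 − 43 = 10 are PR or HI, with the split not given.

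**3. The same share in the azacitidine-magrolimab data (Section 2.2).** ORR was 92% and CR 50%, so all non-CR responders were (92 − 50)/92 = 46% of responders. The mCR share cannot exceed that.

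**4. Illustration of the effect on median DOR.** These inputs are assumed: exponential durations with true median m, the same hazard in all responders, and a share s whose loss of response is recorded d months late. When the result exceeds d, the recorded median is m + (m/ln 2) × ln[1 − s + s × 2^(d/m)]. For m = 8, s = 43/82 and d = 6: 8 + 11.54 × ln(1.3575) = 11.5 months.

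| Share s | m = 8, d = 2 to 6 | m = 12, d = 2 to 6 |
|---|---|---|
| 52% (all mCR, ASTX727-02) | 9.1 to 11.5 | 13.1 to 15.4 |
| 46% (ceiling, azacitidine-magrolimab) | 9.0 to 11.1 | 12.9 to 15.0 |
| 26% (mCR without HI, ASTX727-02) | 8.5 to 9.9 | 12.5 to 13.7 |

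With d = 0, roughly the lowest-value reading, the median does not change.

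**The case against.** A reader might infer that DOR is overstated as planned. The documents do not support that. Lacking a relapse row is not lacking an event: the Failure and Disease Progression rows apply to any responder, the count criterion is measured from best response and needs no prior HI, and the lowest-value reading captures most marrow losses. That part of the objection stands. The Hgb and transfusion criteria are weaker substitutes, since footnote d requires the anemia to be disease-related and Section 8.5.7.1 calls anemia the most common treatment-related event.

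A reader might also infer that half the DOR set has no way to end a response. That fails for the same reason, and the 52% comes from an HMA-monotherapy trial that included CMML, which is excluded here.

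Nor should the point be carried over to PFS. Taken literally, Section 9.3.2 bases PFS on CR subjects, so subjects with mCR only would not be in it; that sentence needs its own clarification.

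It can also be said that DOR is secondary and not formally tested, that the second population sentence is ungrammatical and probably a slip, and that the SAP will supply detail. These limit the consequence but do not remove the defect. Section 9.3 says the SAP will describe the analyses of that section, so it would inherit the two sets, and Table 21 is protocol text.

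**Conclusion.** Section 9.3.2 is wrong as written on duration of CR. If the ORR set were used, 46% (azacitidine-magrolimab mix) to 65% (ASTX727-02 mix) of the subjects in the curve would have had no CR.

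For DOR, the end of response is not fixed for mCR and HI responders. DOR can be overstated if blast progression is read from pretreatment, and little or not at all if it is read from the lowest on-study value. The text does not choose. In the illustration the inflation of the median runs from none to about 3.5 months, and this rests on assumed medians, delays and response mix, including the inferred total of 133. The primary CR rate is unaffected. This should be corrected before the first efficacy look.

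**What to change.** In Section 9.3.2, estimate duration of CR in CR subjects only and DOR in all responders, and also report DOR by response category. State whether PR is among the responders, since the Section 8.3.1 list omits it and the background definition in Section 2.2 includes it.

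For the DOR analysis only:

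- State the start, event and censoring rules.
- Count loss of marrow CR as an event measured from the lowest on-study blast value, and name that value as the reference for the blast strata. Decide explicitly how small rises, such as 4% to 5.5%, are handled.
- Define loss of HI in keeping with Table 21 footnotes c and d, so that transient or treatment-related cytopenias do not count. Simply ceasing to meet the Table 22 criterion would conflict with those footnotes.

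Label these as analysis definitions that leave the treatment-stopping rules unchanged, because Section 4.1 links progression to stopping treatment.

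The cost is wording and programming, with no new assessments. Reported DOR may be somewhat shorter.

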### 9.3.3 Other Analysis

PK analyses will be described in the SAP finalized before database lock. The population PK analysis will be presented separately from the main clinical study report.

## 9.4 Interim Analysis

This is an open-label study. Ongoing analyses to help manage the study and support the DSRC reviews for safety and antitumor activity will be undertaken.

One formal interim assessment of futility is planned after approximately 40 subjects have been treated with the oral decitabine/cedazuridine plus magrolimab and completed a minimum of 6 cycles of treatment. The number of subjects to include in the interim analysis was chosen to minimize the chance of exposing subjects to an ineffective treatment. The expected CR is approximately 40%. However, the expected response rate may be revised once the results of the Phase 3 magrolimab ENHANCE study are available. If the achievement of the expected CR rate is questionable, possible study modification will be discussed with the DSRC.

The decision to continue enrollment will be informed by the observed number of CRs (ie, CRs) and safety of the combination (ie, incidence and severity of adverse events). [Table 16](#) provides the probabilities of observing varying frequency of response under different true response rates for a sample of approximately 40 subjects. For example, observing 8 or fewer responses out of 40 treated subjects would suggest a low likelihood (11% chance) that the true response rate is  $>30\%$  and 0.6% chance that the true response rate is  $>40\%$ . On the other hand, observing 14 or more responses out of the 40 treated subjects would suggest a high likelihood (80% chance) that the true response is greater than 30%. Therefore, when 40 subjects are treated and evaluable for response assessment, if 8 or fewer responses are observed, the study will be discontinued.

Similarly, if a two-stage Simon design is implemented to test whether the proportion responding (P) warrants continuation to the next phase (ie,  $H_0: P \leq 0.2$  versus  $H_1: P \geq 0.3$ ), Type I error rate of 0.05, 80% power, and a total sample size of approximately 100 subjects, at the first stage (n approximately 40) the trial should be discontinued if 8 or fewer subjects respond to the treatment. Otherwise, the study will continue to the next stage.

This calculation will be revised once the results of the Phase 3 magrolimab ENHANCE study are available and the true expected response is confirmed.

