### 9.3.1 General Considerations

All efficacy and safety endpoint parameters will be summarized descriptively. Continuous efficacy and safety endpoints will be summarized using the mean, standard deviation, median, minimum, and maximum, 25 and 75 percentiles). Frequency distributions (counts and percentages) will be used to summarize categorical endpoints.

The primary efficacy analysis will be performed using a 2-sided 0.05 significance level. No adjustments for multiple endpoints is planned.

It is anticipated that statistical summaries will be performed using SAS Version 9.4 or higher (SAS Institute, Inc., Cary, NC, USA) or higher. Additional software may be used to produce graphics and for statistical methodology not available in SAS.

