**Table 16: Probabilities of Observing Varying Frequency of Response Under Different True Response Rates (40 Subjects)**

No. Response (r)	Probability	Event Rate			
		20%	30%	40%	50%
8	Prob(no. resp <= r   true p)	0.593	0.111	0.006	0.000
9	Prob(no. resp <= r   true p)	0.732	0.196	0.016	0.000
10	Prob(no. resp <= r   true p)	0.839	0.309	0.035	0.001
11	Prob(no. resp <= r   true p)	0.912	0.441	0.071	0.003
12	Prob(no. resp <= r   true p)	0.957	0.577	0.129	0.008
13	Prob(no. resp <= r   true p)	0.981	0.703	0.211	0.019
14	Prob(no. resp <= r   true p)	0.992	0.807	0.317	0.040
15	Prob(no. resp <= r   true p)	0.997	0.885	0.440	0.077
16	Prob(no. resp <= r   true p)	0.999	0.937	0.568	0.134

Prob=probability; No.=number.

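### Section 9.4 claims 80% power at a 30% CR rate with about 100 subjects; the exact figure for 40/100 is 73.6%, and 80% needs at least 116 subjects

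*Combined protocol and SAP*

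**What the plan says.** Section 9.4 plans one futility look at about 40 treated subjects. It argues from Table 16 and sets the rule: "Therefore, when 40 subjects are treated and evaluable for response assessment, if 8 or fewer responses are observed, the study will be discontinued". On the favourable side it says that "observing 14 or more responses out of the 40 treated subjects would suggest a high likelihood (80% chance) that the true response" rate is above 30%.

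It then offers a second justification: "Similarly, if a two-stage Simon design is implemented to test whether the proportion responding (P) warrants continuation to the next phase". The null is a CR rate of at most 0.2 and the alternative at least 0.3. The specification is "Type I error rate of 0.05, 80% power, and a total sample size of approximately 100 subjects, at the first stage (n approximately 40", with the same stop at 8 or fewer. No final-stage cutoff is given, and the sidedness of the 0.05 is not stated. The section closes with "This calculation will be revised once the results of the Phase 3 magrolimab ENHANCE study are available".

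Two other places matter. Section 9.1 sizes the study on a 40% CR rate against 20%. Section 9.3.1 says "The primary efficacy analysis will be performed using a 2-sided 0.05 significance level".

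**The concern.** Separating 20% from 30% with 80% power at one-sided 0.05 is a demanding target for 100 subjects, before any loss from a futility stop. If the inputs conflict, a reader who takes the sentence at face value will believe that a true 30% CR rate would be detected eight times in ten, when the design described detects it less often.

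The Table 16 sentence raises a related problem. Its 80% does not match the tabulated complement of 14 or more responses. The 11%, 0.6% and 80% figures are also worded as chances that the true rate exceeds a value, whereas the table gives probabilities of the data at a fixed true rate. These sentences lead directly to the stopping decision.

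**Working it through.** **Inputs (Section 9.4).** p0 = 0.20; p1 = 0.30; alpha = 0.05; n1 = 40; stop if X1 ≤ 8; N = 100. Alpha is read as one-sided, the reading most favourable to the plan. The final cutoff c is not stated, so it is taken as the smallest c whose exact size is at most 0.05.

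**The plan's own table.** For X ~ Bin(40, p), P(X ≤ 8) = 0.593, 0.111 and 0.006 at p = 0.20, 0.30 and 0.40. These agree with Table 16.

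**Power of the Simon design.** With a futility stop only,

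P(success | p) = Σ over x from 9 to n1 of P(Bin(n1, p) = x) × P(Bin(N − n1, p) ≥ c − x).

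At n1 = 40, N = 100:

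- c = 26: size 0.0756, above 0.05; even so, power is only 78.6%
- c = 27: size 0.04996; power at 30% is **73.6%**
- c = 29, the smallest cutoff with size at most 0.025: power 60.3%

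**Allowing for the approximate sizes** (stop kept at 8, c chosen again each time):

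| n1 / N | c | Size | Power at 30% |
|---|---|---|---|
| 40 / 98 | 27 | 0.0406 | 70.3% |
| 40 / 101 | 28 | 0.0351 | 69.3% |
| 41 / 100 | 28 | 0.0320 | 68.1% |
| 37 / 97 | 27 | 0.0335 | 65.3% |
| 44 / 103 | 28 | 0.0464 | 75.2% |

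The last two rows are the minimum and maximum over n1 = 36 to 44 and N = 95 to 105 (median 70.3%). Over n1 = 38 to 42 and N = 98 to 102 the range is 67.3% to 73.6%.

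**What 80% would need.**

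- Searching first-stage sizes and stops, no futility-only two-stage design with N from 95 to 115 reaches 80%; smaller N is ruled out by the bound below. The first that does is N = 116, for example stop at ≤ 13/66 and success at ≥ 31/116: size 0.0475, power 80.07%.
- With 8/40 kept, the first N is 131, with success at ≥ 34: size 0.0492, power 80.2%.

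**Could early stopping for efficacy rescue it?** The most powerful (randomised) 0.05-level test of 0.20 against 0.30 on N subjects bounds every design that uses at most N. Its power is 75.6% at N = 100, 77.3% at N = 105 and 79.9% at N = 113.

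**The statement on 14 or more responses.** At p = 0.30, n = 40:

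- the row for 13 responses reads "0.981 0.703 0.211 0.019"; its 30% entry, P(X ≤ 13) = 0.703, is the complement of 14 or more
- the row for 14 responses reads "0.992 0.807 0.317 0.040"; its 30% entry is P(X ≤ 14) = 0.807
- P(X ≥ 14) = 1 − 0.703 = 0.297

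The 80% therefore appears to come from the row for 14 rather than 13. The probability of 14 or more is 1.9%, 29.7% and 78.9% at true rates of 20%, 30% and 40%.

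**The case against.** The Simon sentence is conditional and gives no final cutoff, so 73.6% describes a test completed here rather than one written in the plan. Its only output is the 8/40 stop, already set from Table 16. The study is sized in Section 9.1 on 40% against 20%, and the section promises revision after ENHANCE. All of this is fair and limits the weight of the point. It does not make the 80% right: no choice of final cutoff gives 80% power at level 0.05 with about 100 subjects, and the promised revision concerns the expected response rate.

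The 65% to 75% range depends on how widely the approximate sizes are read, and its low end is partly a discreteness effect (size only 0.0335 at 37/97). That also stands, so 73.6% at the nominal sizes is the figure to lead with.

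The source of the 80% for 14 or more responses is an inference, since P(X ≥ 14) at a 40% CR rate is 78.9%, also close to 80%. Under either origin it is not a probability that the true rate exceeds 30%. Table 16 does label its entries as conditional on the true rate, so a careful reader could notice the slip.

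**Conclusion.** The concern holds and is minor. At the nominal 40/100 the power at a 30% CR rate is 73.6%, which is 6.4 points below the stated 80%, and about 65% to 75% for nearby sizes. This assumes exact binomial calculation, a one-sided 0.05 level and the smallest admissible final cutoff; a two-sided level makes the shortfall larger. The 80% attached to 14 or more of 40 responses is also wrong as worded.

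The values of Table 16 and the 8/40 stop are not affected. Nor is the Section 9.1 claim: the exact 95% lower bound exceeds 20% at 29 or more CRs in 100, and at a 40% CR rate that criterion has 98.7% power with the futility look included.

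**What to change.** Keep N, the 8/40 rule and the primary analysis. In Section 9.4:

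- Delete the claim of 80% power at a 30% CR rate. This is the cleaner option. If the Simon statement is kept with a power, give it as 73.6% at 40/100 (about 65% to 75% depending on the exact sizes), with one-sided alpha 0.05 and success at 27 or more CRs. Say that this cutoff serves the Simon statement only, because the primary criterion needs 29 or more of 100 and Section 9.3.1 uses a two-sided level.
- Replace the Table 16 sentences with wording such as: 8 or fewer responses occur with probability 59.3%, 11.1% and 0.6%, and 14 or more with probability 1.9%, 29.7% and 78.9%, if the true CR rate is 20%, 30% and 40% respectively.

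The cost is a text correction, with the power at 30% either removed or shown as less favourable. The same wording should be carried into the SAP, which Section 9.3 says will be finalised before the futility look.
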